7.7.3. Additional Objectives

The following additional analyses will be conducted. Additional procedural characteristics, including treatment duration, frequency of distal renal artery treatment, ablations per vessel, location of ablations, number of ablations per patient, number of applications per patient (1 application is defined as “<4 ablations delivered simultaneously”) and other characteristics will be presented with descriptive statistics to assess their impact on blood pressure. These additional analyses will be presented for the ITT study population defined in section 7.1.3.1.

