Medtronic has developed a radiofrequency catheter with multiple electrodes, as a minimally invasive means of achieving renal sympathetic denervation. Bilateral renal denervation will be performed using a percutaneous, catheter-based system that delivers radiofrequency (RF) energy through the luminal surface of each renal artery at four locations simultaneously. In comparison to the previous single-electrode Symplicity™ renal denervation system, the multi-electrode catheter provides the physician with a pre-defined and consistent ablation pattern that is intended to improve the accuracy of treatment. The RF energy may be delivered to up to 4 electrodes simultaneously. If the physician elects to complete multiple treatments in one artery, subsequent treatments are easily accommodated by re-positioning the catheter proximally (at least 5 mm) and de-selecting electrodes via the graphical user interface on the Symplicity G3 generator. The electrodes are mounted on to a self-expanding Nitinol shaft that takes a spiral configuration allowing electrode contact with the vessel wall. An evaluation of the results of pre-clinical (*in-vivo*) and *in-vitro* testing supporting the use of the Symplicity Spyral catheter and Symplicity G3 generator as investigational devices in human subjects is included in the Investigator's Brochure. Medtronic has performed a comprehensive set of bench testing and preclinical studies that have shown that this manner of low-power ablation produces distinct, focal, sterile lesions that subsequently heal, resulting in no clinically relevant long-term sequelae to either the vessel or the kidney.

The currently ongoing SPYRAL PIVOTAL – SPYRAL HTN-OFF MED and SPYRAL HTN-ON MED studies are multi-center, international, single blind, randomized, sham-controlled studies designed to evaluate the effect of renal denervation on blood pressure. The SPYRAL PIVOTAL – SPYRAL HTN-OFF MED study is evaluating the effect of renal denervation in the absence of antihypertensive medications, whereas the SPYRAL HTN-ON MED study is evaluating the effect of renal denervation on standard medical therapy.

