For the primary efficacy endpoint of changes from baseline in 24-h systolic blood pressure at three months, there was a significant difference between the renal denervation and sham procedure groups. This endpoint was met with a posterior probability of superiority greater than 0.999 and a treatment difference of -3.9 mm Hg (95% BCI -6.2 to -1.6). For the secondary efficacy endpoint of difference in three-month changes in office systolic blood pressure between the two groups, the difference was significant, and the endpoint was met (difference -6.5 mm Hg (95% BCI -9.6 to -3.5), with posterior probability of superiority of more than 0.999. The blood pressure changes analyzed using the prespecified ANCOVA-adjusted frequentist analysis of the overall population show similar changes in blood pressure to Bayesian results.

Besides the “confounding factors” analysis of SYMPLICITY HTN-3 indicating that the blood pressure response to renal denervation may depend on the number of lesions applied, few studies have shown a strong relationship between the number of lesions delivered and subsequent blood pressure reduction. These new results indicate that the location of the lesion, i.e., the distal main and branches, may be an important factor in blood pressure reduction.

Both SPYRAL HTN-OFF MED and SPYRAL HTN-ON MED trials used the same RDN technique, applying treatments in eligible renal arteries and the branches, and presented similar results in three and six months follow-up, respectively. In the SPYRAL HTN-OFF MED trial, on average  $17.9 \pm 10.5$  ablations were performed in the main renal arteries, and an additional  $25.9 \pm 12.8$  ablations were performed in branch vessels.

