#### **9.1.5.2. Denervation Procedure**

The renal artery denervation procedure will be performed according to the supplied Symplicity Spyral catheter *IFU*, Symplicity G3 generator *User Manual* and associated training provided by Medtronic. Pre-treatment with both anxiolytic medications and analgesic medications, such as morphine sulfate or fentanyl (with additional doses timed with ablation treatments as appropriate) should be considered. Blood pressure, O2 saturation, and heart rate should be closely monitored both during the procedure and throughout the recovery phase from the conscious sedation administered.

The goal of the denervation procedure in this protocol is to ablate renal nerves where they are in close proximity to the vessel lumen by delivering RF energy in a helical pattern in the distal main renal artery and branch vessels coming off the main renal artery (first order branches).

[figure not shown]
The following are required:

- Placement of the catheter in each accessible renal artery branch vessel coming off the main renal artery to achieve  $\leq 4$  lesions in a helical pattern and
- Placement of the catheter in the most distal, treatable portion of the main renal and/or renal accessory arteries to achieve  $\leq 4$  lesions in a helical pattern

Note 1: Initial placement of the Symplicity Spyral catheter should not extend into the renal parenchyma as identified on fluoroscopic imaging.

Note 2: Depending on anatomy, branch and main renal artery should be treated with the goal of applying 4 ablations in each location.

Note 3: Uncommon subject anatomy variations may be treated per investigators discretion in accordance with protocol guidelines and procedural training.

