7.2. General Methodology

Descriptive statistics of continuous measures will be presented and include sample size, mean, standard deviation, median, first and third quartiles, minimum and maximum. For categorical outcomes, the number and percentage of subjects in each category will be presented. Paired t-tests will be used to compare changes in continuous measures from baseline to follow-up. All statistical analyses will be performed using SAS for Windows (version 9.4 or higher) or other widely accepted statistical or graphical software. Subject data listings and tabular or graphical presentations of results will be provided.

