7.6. Treatment and Anti-hypertensive Medications Characteristics

Renal denervation treatment measures will be summarized separately for each kidney, and combined. Anti-hypertensive medication use will also be summarized at baseline and at each follow-up.

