7.9. Subgroup Analyses

No subgroup analysis will be performed.

This document is electronically controlled. Printed copies are considered uncontrolled.

Confidential

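### SAP 7.7.3 aims to assess how procedural characteristics affect blood pressure but specifies no analysis that could show it, and its definition of an application, as printed, leaves out a full four-electrode delivery

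*SAP*

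**What the plan says.** SAP 7.7.3 (Additional Objectives) lists treatment duration, frequency of distal treatment, ablations per vessel, location of ablations, ablations per patient and applications per patient. It says that these and "other characteristics will be presented with descriptive statistics to assess their impact on blood pressure". The population is the ITT set. In the same sentence, one application is defined as "<4 ablations delivered simultaneously".

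Other places that bear on this:

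- SAP 7.2: "Descriptive statistics of continuous measures will be presented and include sample size, mean, standard deviation, median, first and third quartiles, minimum and maximum". Categorical outcomes get counts and percentages. Paired t-tests compare a measure with its own baseline.
- SAP 7.6: "Renal denervation treatment measures will be summarized separately for each kidney, and combined". BP is not mentioned.
- SAP 7.9: "No subgroup analysis will be performed".
- Protocol 4.2.3 plans a different additional analysis: a comparison of procedural characteristics between DYSTAL and HTN-OFF MED.
- Protocol 3.1, on the device: "The RF energy may be delivered to up to 4 electrodes simultaneously". Protocol 6.3 lists the firing of all four electrodes together as a generator feature.
- Protocol 9.1.5.2 asks for up to and including four lesions per catheter placement, and its Note 2 says that "branch and main renal artery should be treated with the goal of applying 4 ablations in each location".

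**The concern.** There are two separate defects in one paragraph.

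**Aim and method do not match.** A statement about impact on BP needs a BP variable and some measure that links it to the procedural variable. SAP 7.7.3 supplies neither. Any association that is reported would have to be chosen after the data are in hand, although SAP section 3 gives the document's purpose as setting out the analyses prospectively and in detail. The subject matters to the sponsor's reasoning. Protocol 3.1 notes that "few studies have shown a strong relationship between the number of lesions delivered and subsequent blood pressure reduction" and argues that lesion location may be what counts.

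**The counting rule conflicts with the procedure.** Read as printed, the definition requires strictly fewer than four simultaneous ablations. The delivery that the protocol treats as the goal would then not be an application, and a more completely treated subject would have a lower count.

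**Working it through.** **1. Is BP linked to a procedural variable anywhere in the SAP?**

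| Section | Procedural variable | BP variable | Link between them |
|---|---|---|---|
| 7.2 | none named | none named | none; one-variable summaries and paired t-tests |
| 7.6 | yes, by kidney and combined | none | none |
| 7.7.2.1 | none; covariates are baseline BP, age, gender, BMI, diabetes | 3-month endpoints | cohort effect only |
| 7.7.3 | yes | only the words of the aim | none specified |
| 7.9 | not mentioned | not mentioned | subgroup analyses ruled out |

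No section specifies the link. SAP 7.7.3 states no sample size, power or error rate, so it has no figure of its own to reproduce.

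**2. The application count.** Under the printed rule, a delivery of k ablations counts only if k < 4. For k = 4 the condition fails.

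- Ten deliveries of four and two of three: printed rule 0 + 2 = 2; with 4 or fewer, 10 + 2 = 12.
- Twelve deliveries, with an assumed share f using all four electrodes: printed count = 12 × (1 − f). For f = 25%, 50%, 75% and 100% this gives 9, 6, 3 and 0. With 4 or fewer, the count is 12 each time.

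The documents do not give the share of four-electrode deliveries, so f is shown as a range.

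**3. What an exploratory association could resolve.**

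*SD of the change in 24-h SBP.* Inputs from Protocol 13.3 and SAP section 6: n = 38, mean −5.5, 95% CI −9.1 to −2.0, p = 0.003.

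- Half-width = (9.1 − 2.0)/2 = 3.55.
- SE = 3.55 / t(0.975, 37 df) = 3.55/2.026 = 1.75.
- SD = 1.752 × √38 = 10.8 mmHg.
- Check: t = −5.5/1.752 = −3.14, two-sided p = 0.0033, which agrees with the stated 0.003.

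*Slope per 1 SD of an ablation count.* The 95% half-width is 1.96 × SD × √(1 − ρ²) / √(n − 2), where ρ is the correlation of the BP change with baseline BP. The documents do not give ρ; 0.4 is assumed.

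- n = 50, ρ = 0.4: 1.96 × 10.8 × √0.84 / √48 = 2.8 mmHg.
- n = 50, ρ = 0 and 0.6: 3.1 and 2.4 mmHg.
- n = 38 with BP data, ρ = 0.4: 1.96 × 10.8 × √0.84 / √36 = 3.2 mmHg.
- Two counts entered together and correlated at r (assumed): divide by √(1 − r²). For r = 0.5, 2.8/0.866 = 3.2 mmHg; for r = 0.8, 2.8/0.6 = 4.7 mmHg.

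*As a simple correlation* (Fisher z): 80% power at two-sided 0.05 needs |r| = tanh((1.960 + 0.842)/√(n − 3)). This is 0.39 at n = 50 and 0.44 at n = 38. The 95% interval around r = 0 is about ±0.28 and ±0.32.

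**The case against.** **BP is not excluded.** A reader might infer that SAP 7.7.3 rules out BP data, so that its tables could not change with the outcome. The text does not say that. It is silent on how BP would enter, and a descriptive display by BP response would fit its wording. This stands, and it limits the point to an analysis that is unspecified. It does not rescue the stated aim, because silence leaves the choice until after the data are seen.

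**The approach is tested elsewhere.** A reader might infer that SAP 7.7.3 is the only test of lesion location against BP. It is not. The propensity-stratified comparison in SAP 7.7.2.1 tests the distal-plus-branch approach as a whole, with BP change as the outcome. Within DYSTAL all treatment is directed to the distal main artery and first-order branches, so the contrast in location is limited. Both points stand.

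**The sign may be a slip.** Protocol 9.1.5.2 prints four-or-fewer for the same placements. An inequality sign is visibly corrupted in exclusion criterion 12 of the Protocol synopsis, where section 8.4 prints it correctly. Against this, the SAP prints such signs correctly in 7.1.3.1 and Appendix IV. The matter cannot be settled from the text. It would be wrong to infer that the reported counts will be wrong in practice: generator data are downloaded, and SAP section 8 requires independent double programming. If the source has the correct sign, this half falls and the first is untouched.

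**No protocol objective requires a regression.** True. Deleting the clause is therefore an equally acceptable remedy.

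**Conclusion.** The concern holds as a minor one. SAP 7.7.3 states an aim for which neither it nor any other SAP section gives a BP variable, time point or measure of association, and the summaries in SAP 7.2 cannot meet that aim. The printed definition of an application conflicts with Protocol 3.1, 6.3 and 9.1.5.2, on the condition that the printed sign is the source text.

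The consequence is confined to an additional analysis in a study with no powered endpoints or formal hypotheses (SAP 7.4). No efficacy or safety endpoint changes.

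The half-width of about 2.8 mmHg per SD is a best case for the 50 treated subjects: one predictor uncorrelated with the others, no missing BP, ρ = 0.4, and the same SD as in the 38 subjects of the first phase. Any result would be exploratory.

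A reader might infer that adding the HTN-OFF MED denervation arm would give much better precision. The documents do not support a figure for this. The 166 denervation subjects in Protocol 3.1 cover the pilot and pivotal cohorts, whereas SAP Table 1 adds a secondary cohort whose size is not given. Main-artery ablation count is also tied to cohort by design.

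**What to change.** In SAP 7.7.3:

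1. Define one application as one simultaneous delivery of 1 to 4 (≤4) ablations.
2. Choose one of the following:
   - Delete the clause about impact on blood pressure, so that the section promises only a description of the procedure.
   - Replace it with an exploratory linear regression in treated DYSTAL subjects. The outcome is the 3-month change in 24-h SBP, repeated for office SBP. The predictors are the number of distal-main ablations and the number of branch ablations, entered together, with adjustment for the matching baseline BP. Report slopes with 95% CIs and make no causal claim, because ablation number depends on anatomy.

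The restriction to treated subjects should be explicit. The ITT set is all enrolled subjects, about 350, of whom about 350 − 50 = 300 (86%) would have no denervation data.

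The cost is two wording changes and, under the second option, one table from data already collected (procedure and generator data under Protocol 9.1.5.3, BP at the 3-month visit). No extra subjects, visits or procedures are needed.

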7.8. Safety Evaluation

Adverse Event (AE) information will be collected by the site from subject enrollment (consent) through study termination or study exit (AEs up to 6 months follow-up, SAEs up to 12 months follow-up). AEs will be followed until the event has resolved (in the case of permanent impairment, the event will be followed until it stabilizes and the overall clinical outcome has been ascertained), subject exit or study termination.

The Investigator will report any adverse events that may occur to the Sponsor, and will assess seriousness, relationship (to the device, procedure and renal denervation therapy where applicable), subsequent intervention required, resolution status and whether the adverse event resulted in the subject’s discontinuation from the study. The Investigator will provide further information regarding adverse events as requested by the Sponsor.

7.9. Subgroup Analyses

No subgroup analysis will be performed.

This document is electronically controlled. Printed copies are considered uncontrolled.

Confidential

7.10. Changes to Planned Analysis

There are no changes to the planned analysis at this time.

8. Validation Requirements

Two statistical programmers will work independently to produce and validate all the tables, listings and graphs for the study reports.

This document is electronically controlled. Printed copies are considered uncontrolled.

Confidential

9. COVID-19 Related Analyses

In accordance with FDA guidance document “FDA Guidance on Conduct of Clinical Trials of Medical Products during COVID-19 Pandemic” [1], we will provide AE and SAE tables summarizing the site-reported adverse events attributed to COVID-19 in separate tables.

10. References

[1] FDA Guidance on Conduct of Clinical Trials of Medical Products during COVID-19 Pandemic. Guidance for Industry, Investigators, and Institutional Review Boards. March 2020.

This document is electronically controlled. Printed copies are considered uncontrolled.

Confidential

11. Statistical Appendices

11.1. Appendix I: Imputation of AE Onset or Anti-Hypertensive Medication Start Dates

The table below specifies how to input missing dates for AE onset or anti-hypertensive medication start dates:

Valid Portion	Missing Portion	Imputed Value for Missing Portion
Month, Year	Day	Set Day = first day of that month and year, then set the day = later of (new onset date, informed consent date).
Year	Day, Month	Set date = later of (January 1st of that year, informed consent date).
None	Day, Month, Year	Informed consent date

This document is electronically controlled. Printed copies are considered uncontrolled.

Confidential

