### 8.2. Subject Enrollment

Subjects will be pre-screened for potential enrollment in the clinical study based on prior medical history and records of office systolic blood pressure.

A subject is considered enrolled in this clinical study at the time at which the subject and investigator or authorized designee have personally signed and dated the Patient Information and Informed Consent Form. Written informed consent must be obtained prior to Screening Visit 1.

Investigational sites will maintain a subject identification log; however, this document will not be submitted to the sponsor.

It is anticipated to enroll approximately 350 subjects to reach approximately 50 renal denervation treated subjects within this study.

Each site will receive a supply of single-use catheters. A minimum of 50 single use catheters will be required to treat approximately 50 subjects. It is anticipated that a small number (<10%) of catheters will need to be replaced due to damage or contamination. Sites will be expected to return all unused study product to Medtronic.

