### **9.1.4. Screening Visit 2**

Screening Visit 2 must occur within three to four weeks of completion of SV1. The following assessments will be performed at Screening Visit 2:

- a) **Clinical assessment** will be conducted to further evaluate for prior or existing medical conditions that would exclude subjects from participation in the study and to establish the subject's baseline medical condition. An individual experienced in performing histories and

physical exams is required to assess subjects for safety assessment during the period of time that study subjects are not on antihypertensive medications.

- b) **Office blood pressure measurements** will be obtained in accordance with **Appendix 16.5**. The average office blood pressure value will be used as the baseline value for comparison with follow-up visit office blood pressure values. Subjects with an office systolic blood pressure  $\geq 150$  and  $< 180$  mmHg and an office DBP  $\geq 90$  mmHg are eligible to continue the screening process.
- c) **Laboratory tests:**
  - **Basic metabolic panel Chem-7 (blood):** serum-creatinine, sodium, potassium, blood urea nitrogen (BUN) or urea, bicarbonate, chloride, and glucose. Bicarbonate will not be measured for subjects enrolled in Europe.
  - **eGFR** will be calculated from the serum-creatinine in the Chem-7 panel for eligibility criteria by using the 4 variable Modification of Diet in Renal Disease (MDRD) Formula **Note:** If eGFR  $\geq 42$  and  $< 45$  mL/min/1.73m^2 then subject can be retested after hydration with a single, repeat test within two weeks.
  - **hCG pregnancy test in blood/urine** for female subjects who are not postmenopausal. (This may also be completed the day of the procedure).
  - **Drug testing (urine/blood)** to ensure medications are no longer present in the subject's system. A urine sample will be collected, preferably using the subject's first morning urine. A blood sample will be collected at the time of the visit. Drug testing samples collected for subjects that screen fail after obtaining the sample, must not be sent to the core lab for analysis.

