  - **24-hour ABPM** will be applied at the conclusion of Screening Visit 2 to confirm subject's baseline blood pressure. This value will be utilized as the baseline value for calculating change in 24-hour ABPM at various time points post-procedure. Subjects with a 24-hour systolic ABPM of  $< 140$  or  $\geq 170$  mmHg after completion of the screening visit will be exited from the study. Subjects with a 24-hr systolic ABPM of  $\geq 140$  and  $< 170$  mmHg are eligible to continue to the procedure visit. A single repeat measurement is allowed in case of the following: 1.) a technical issue with the blood pressure monitor or failure to follow ABPM instructions, or 2.) if a valid number of readings is not obtained, or 3.) if the 24-hr systolic ABPM measured 135 -  $< 140$  mmHg or 170-175 mmHg. ABPM must be conducted according to the guidelines in **Appendix 16.5**. If ABPM is repeated office blood pressure and drug testing must be repeated on day the ABPM is applied.
  - **Adverse event reviews** will be completed to document adverse events that occur after enrollment.

Subjects determined to not be eligible for renal angiogram will be exited from the study, as described in the **Subject Exit from Study section 9.5.1** of this CIP.

It is expected that subjects who are eligible to continue to the renal angiogram will be scheduled for a procedure date within 14 calendar days of completion of Screening Visit 2. Completion of Screening Visit 2 is defined as the day the 24-hour ABPM is completed or date of lab results, whichever is later. No subjects will be eligible for the renal angiogram more than two weeks following Screening Visit 2.

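### Incomplete AE onset and antihypertensive start dates are imputed with consent as the only floor, so some post-procedure AEs are dated before the procedure and some later drug restarts into the off-drug period

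*SAP*

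**What the plan says.** SAP 11.1 (Appendix I) has one table that "specifies how to input missing dates for AE onset or anti-hypertensive medication start dates". It has three rules:

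- Day missing: take the first of the known month, "then set the day = later of (new onset date, informed consent date".
- Day and month missing: "Set date = later of (January 1st of that year, informed consent date".
- Whole date missing: use the consent date.

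Consent is the only floor. The procedure date, the 3-month visit and the visit at which the item was first reported play no part.

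On where consent lies, Protocol 8.2 says "Written informed consent must be obtained prior to Screening Visit 1". Protocol 9.1.4 adds "Screening Visit 2 must occur within three to four weeks of completion of SV1" and "No subjects will be eligible for the renal angiogram more than two weeks following Screening Visit 2".

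On use of the dates, SAP 7.6 says "Anti-hypertensive medication use will also be summarized at baseline and at each follow-up". SAP 7.8 has AEs collected from consent onward. SAP 7.3 states that missing data are not imputed and does not mention Appendix I.

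**The concern.** Consent is a sensible floor for a study in which treatment starts at enrolment. Here a washout of three to four weeks and a second screening visit lie between consent and the procedure. A date moved back to the first of the month, to 1 January or to consent can therefore cross the procedure.

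For AEs, the split at the procedure is needed to read device safety. AEs accrue from consent, about 350 subjects are enrolled to treat about 50, and Protocol 11.1 ties procedure-relatedness to onset within seven days afterwards. That first week is where a missing day is most often misplaced.

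For drugs, the off-drug period runs through the 3-month visit, and planned re-introduction begins once that visit's ABPM is complete (Protocol 9.1.6 and 9.1.10). A start date moved back to the first of the month would often cross that visit, so a table built from start dates would show use during a period when the subject took none.

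**Working it through.** The plan states no figure for this rule, so there is none to reproduce. The check applies the three rules literally to every procedure date in a 365-day year.

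**Consent to procedure.** SV1 to SV2 is 21–28 days. The procedure is at most 14 days after SV2 is complete. If consent is on the day of SV1 and the ABPM finishes the day after SV2, the lag is 21 + 1 = 22 to 28 + 1 + 14 = 43 days. The shares below are the same for both lags, because any positive lag puts the floor before the procedure.

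**AEs, day missing.** An AE on day *d* is dated before the procedure if it falls in the same calendar month and the procedure was not on the 1st. For *d* up to 27 the share of procedure dates is [365 − 12(*d* + 1)] / 365. For *d* = 28, 29 and 30 it is 18/365, 7/365 and 0.

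**AEs, day and month missing.** The share is [365 − (*d* + 1)] / 365.

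**AEs, whole date missing.** The share is always 100%.

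| Onset day after procedure | Day missing | Day and month missing |
|---|---|---|
| 0 | 353/365 = 97% | 99.7% |
| 7 | 269/365 = 74% | 98% |
| 14 | 185/365 = 51% | 96% |
| 21 | 101/365 = 28% | 94% |
| 30 | 0% | 92% |
| 90 | 0% | 75% |
| 180 | 0% | 50% |

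Averages for a missing day, with onset spread evenly over the range:

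- Days 0–7: (8 × 365 − 12 × 36) / (8 × 365) = 2488/2920 = 85%.
- Days 0–30: (28 × 365 − 12 × 406 + 18 + 7) / (31 × 365) = 5373/11315 = 47%.
- Days 0–180: 5373 / (181 × 365) = 8%.

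**Drug restarts.** The same formulas apply, with *d* counted from the 3-month visit. With the day missing, a restart is dated before that visit for 93% of dates if it came 1 day later, 74% at 7 days, 51% at 14 days and 0% at 30 days. With day and month missing the shares are 99.5% at 1 day and 92% at 30 days. With the whole date missing the restart is always dated to consent, hence before baseline.

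With day and month missing, the date becomes consent if the restart year is the consent year. Otherwise it becomes 1 January, which need not precede baseline. For a restart on day 97, consent is 119 to 140 days earlier, so the years agree for (365 − 119)/365 = 67% to (365 − 140)/365 = 62% of dates.

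**Example.** Consent is on 14 May and the procedure on 20 June. An AE on 25 June with the day missing becomes 1 June, 19 days before the procedure. With no date it becomes 14 May. A drug restarted on 20 September, after a 3-month visit on 18 September (day 90), becomes 1 September (day 73), or 14 May if the month or the whole date is missing.

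**The case against.** The strongest reply is that little depends on these dates.

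- **Adjudicated events.** SAP 7.7.1 counts events up to the evaluation day and states no lower bound at the procedure, so a back-dated event stays in the numerator. The creatinine endpoint is not adjudicated, but it uses laboratory dates (SAP Appendix V).
- **AE tables.** The SAP specifies no AE table split at the procedure. Investigator and sponsor classify relatedness (Protocol Table 8), and nothing derives it from an imputed date.
- **Efficacy.** Per-protocol compliance uses blood or urine drug testing (SAP 7.1.3.3). Escape is defined by confirmed office SBP or safety reasons. SAP 7.6 does not say that its summary is built from start dates.
- **Frequency.** Subjects stay overnight after the procedure and have contacts at 2 weeks, 1 month, 6, 8 and 10 weeks and 3 months. Investigators must date each event, and restarts are documented on the CRF. The day-missing share is 8% over days 0–180.

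All of this stands as a limit on the consequences, and it rules out two stronger readings.

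A reader might infer that the rule favours the device on safety. The documents do not support this, because the only specified event-rate algorithm keeps back-dated events. Earlier dating can also pull a later event into an earlier window: with the day missing, a day-45 event is dated to day 30 or before for (365 − 12 × 15)/365 = 51% of procedure dates.

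A reader might also infer that the 3-month efficacy result is undermined. No efficacy set or estimate is stated to use an imputed start date, and a false early start makes off-drug compliance look worse, not better. The ITT last-observation rule does stop at an escape date whose derivation the SAP leaves open, but nothing says it comes from the drug start date.

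What the reply does not remove is that the rule as written yields dates known to be implausible, and nothing else in either document corrects them.

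**Conclusion.** The point holds as a minor defect in a date-handling rule. It affects AE timing relative to the procedure and, if they are built from start dates, the medication-use summaries at baseline and each follow-up. It does not remove events from the adjudicated composite or change per-protocol membership.

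The shares are conditional on a date being incomplete. They assume procedure dates spread evenly over a non-leap year and, for the averages, onset spread evenly over the stated days. With only the day missing, the shift needs the AE to share a calendar month with the procedure, or the restart to share one with the 3-month visit. The documents do not give the number of incomplete dates. It is probably small, so the effect on the trial's tables cannot be computed.

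**What to change.** In Appendix I, set the imputed date to the latest of:

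- (a) the date given by the current rule;
- (b) the last visit at which the event was not reported, or the drug was recorded as not taken;
- (c) for AEs in treated subjects, the procedure date, unless the record (visit of first report, known month or year, or end date) shows onset before the procedure.

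Add that an imputed date may never contradict the known date parts or fall after the visit at which the item was first reported. State also that a drug start imputed to a visit date counts as after that visit. SAP 7.3 should name Appendix I as an exception.

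With the procedure-date floor, the share of post-procedure AEs on days 0–180 dated before the procedure falls to 0% under all three rules. In the example, (b) moves the restart from 1 September to 18 September, the date of the 3-month visit.

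The cost is a few lines of text. Medication and event review is already scheduled at every visit in Protocol Table 1, so no new data are needed. The downside is that an undated AE from the washout may be counted as post-procedure, which is the conservative direction for device safety.
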